### **7.5.2 Safety criteria for suspension of dosing**

For subjects experiences adverse events the following criteria will be used to determine whether the individual or the entire trial should be discontinued.

#### For individual patients

In the event of a Grade 3 or higher adverse event attributable to treatment with APIXABAN and not related to the underlying disease, administration of APIXABAN will be suspended in the patient to allow analysis and determination whether to continue the treatment, alter dosing regimen or to exclude the patient from further participation in the study; if there is any increase in cerebral microbleeds (CMB) at day 14, in either arm, all study medication will be suspended until a repeat MRI is performed 48 hours from day 14 MRI. Study medication will be restarted in clinically stable individuals. In subjects who have a CT scan at day 14 and have a asymptomatic intracranial hemorrhage, all study medication will be suspended until a repeat CT is performed at 48 hours from the day 14 scan. Sstudy medication will be restarted in clinically stable individuals. If subjects experience any symptomatic hemorrhagic transformation in either arm, study medication will be suspended. All subjects will continued to be followed up monthly either by phone or clinic contact until the end of study.

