## 5.7 Subject Completion/Early Withdrawal

It will be documented whether or not each subject completed the clinical study. A subject is considered to have completed the study if he/she has taken all study medications for 6 months and has completed 6 month study assessments or withdrew from the study due to the occurrence of a recurrent embolic stroke, hemorrhagic transformation or death. If a subject does not complete the treatment phase, their data will be used for efficacy and for any safety analysis.

It is understood that withdrawals may occur during a trial. Each subject has the right to withdraw from the trial at any time for any reason without affecting the right to treatment by the investigator. Subjects who do not complete the treatment phase for other reasons then mentioned above, should be followed at day 14 and EOS visits, if possible. At minimum these patients should have a monthly phone call to assess AE/SAE and vital status if they are unable to continue follow-up in clinic.

Subjects needing to withdraw prior to the completion of the study and who do not agree to continue in follow-up should return to the clinic for completion of early withdrawal procedures, as outlined in table 1.

Reasons that a subject may discontinue the study include the following:

- Adverse events including recurrent stroke or hemorrhagic transformation
- Intercurrent illnesses
- Any significant new medical condition
- Protocol violation
- Non-compliance to study medication regimen

- Use of any investigational drug other than the study medication
- Intake of prohibited medication
- Pregnancy
- Subject withdrew consent or lost to follow-up
- Other (reason to be documented)

Withdrawals due to intercurrent illnesses or AEs will be fully documented in the CRF with the addition of supplementary information if available and/or appropriate. Withdrawals due to non-attendance will be followed-up by the investigator to obtain the reason for non-attendance.

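### Section 7.5.2 allows exclusion from the study, not only from drug, after a Grade 3+ apixaban-related event, in conflict with its own closing sentence and with 5.7

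*Combined protocol and SAP*

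**What the plan says.** Section 7.5.2 opens by saying that "the following criteria will be used to determine whether the individual or the entire trial should be discontinued". Under the heading for individual patients, the first trigger is "In the event of a Grade 3 or higher adverse event attributable to treatment with APIXABAN and not related to the underlying disease". Apixaban is then suspended while one of three outcomes is chosen: continue, or "alter dosing regimen or to exclude the patient from further participation in the study". The paragraph goes on to rules for microbleeds and symptomatic hemorrhagic transformation, both written for either arm, and ends: "All subjects will continued to be followed up monthly either by phone or clinic contact until the end of study".

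Section 5.7 lists adverse events among the reasons for discontinuing, with no restriction by arm. Patients who do not complete treatment, for reasons other than recurrent embolic stroke, hemorrhagic transformation or death, "should be followed at day 14 and EOS visits, if possible". The minimum is a "monthly phone call to assess AE/SAE and vital status if they are unable to continue follow-up in clinic". The early-withdrawal (EW) visit is for those "who do not agree to continue in follow-up should return to the clinic for completion of early withdrawal procedures". For patients who do not complete treatment, "their data will be used for efficacy and for any safety analysis".

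Sections 6.5 and 6.6 include MRI or CT at both the EOS and the EW visit, and 5.5 and the schedule of procedures agree. Section 7.2 takes intracranial bleeds from scans at day 14 and EOS, or at an outcome event. Section 8.1.3 codes intracranial hemorrhage as present or absent at 30 and 180 days.

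**The concern.** Stopping a drug and leaving a study are different things, and the 7.5.2 option is worded as the second. A patient can be taken off apixaban for safety and still attend visits and be scanned. A patient excluded from participation may not be, even without having withdrawn consent.

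After baseline the only scheduled scans are at day 14 and at EOS or EW. If the EOS scan is lost, an asymptomatic bleed after the last scan goes unseen, because a phone call about adverse events and vital status cannot detect it. An EW scan cannot show a bleed that happens after it.

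The trigger in 7.5.2 is an event judged to be caused by one arm's drug, in an open-label trial. Any EOS scan lost by this route is therefore missing for a reason related to treatment, in the comparison that is meant to show that early apixaban does not increase intracranial hemorrhage (3.3).

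**Working it through.** The plan gives no figure on this point to reproduce. The check is a comparison of text, followed by simple upper limits.

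**Text**

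1. Does the wording go beyond stopping drug? Yes. The exclusion option refers to participation in the study, and the opening sentence of 7.5.2 speaks of discontinuing the individual.
2. Does it conflict with the closing sentence of 7.5.2? On a plain reading, yes. That sentence covers all subjects to the end of the study and states no exception. It mentions phone or clinic contact but no scan.
3. Does it conflict with 5.7? Yes. An adverse event is a listed reason in 5.7, and a patient who has not refused follow-up is directed to the EOS visit if that can be done. Section 7.5.2 does not refer to 5.7.
4. Is the EOS scan secured if 5.7 is followed? Only in part. The visit is qualified, and the minimum is a call with no imaging.
5. Which outcome depends on the scan? Intracranial hemorrhage by 180 days (3.3, 7.2, 8.1.3).

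**Upper limit on the hemorrhage proportion in the apixaban arm**

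Inputs: 120 patients at 1:1 give 60 per arm (4.1); 8.1.5 uses 50 per group. The number of excluded patients without an EOS scan, k, is not in the documents; 1 to 3 is assumed for illustration. A patient with unknown status could be 0 or 1, so the uncertainty is k/n. This limit is reached only if no bleed has already been recorded for that patient at day 14, at EW or at an outcome event.

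| k | k/60 | k/50 |
|---|---|---|
| 1 | 1.7 points | 2.0 points |
| 2 | 3.3 points | 4.0 points |
| 3 | 5.0 points | 6.0 points |

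**Time with no later scan if an EW scan at day t replaces the EOS scan**

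Days not covered = 180 − t; share = (180 − t)/180. The values of t are illustrative.

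- t = 30: 150 days, 83%
- t = 60: 120 days, 67%
- t = 90: 90 days, 50%
- EOS scan at day 180: 0 days

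**The case against.** The strongest reply is that 5.7 already supplies the rule. A reader of 7.5.2 alone might infer that nothing in the documents says whether an excluded patient keeps the EOS scan. The documents do not support that. Section 5.7 names adverse events as a reason to discontinue, reserves the EW route for those who refuse follow-up, and sends the others to the EOS visit where feasible. Both visits include MRI or CT. This stands. What remains is that 7.5.2 gives a contrary instruction, does not point to 5.7, and 5.7 allows a phone-call minimum.

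The closing sentence of 7.5.2 could be read as covering only the patients with symptomatic transformation in the sentence before it. The contradiction inside 7.5.2 then disappears, but the excluded patient has no follow-up rule in that section and the conflict with 5.7 is unchanged.

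A reader might also infer that only the apixaban arm can lose patients in this way. That is too strong. Section 7.5.2 writes the exclusion for apixaban only, but 5.7 allows discontinuation for adverse events in both arms, so warfarin patients can miss EOS scans too.

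Finally, a reader might infer that the primary analysis is compromised. Section 7.1 does list new hemorrhagic stroke, which under 2.3.2.2 includes asymptomatic imaging findings. But the primary objective (3.2) and the primary analysis (8.1.2) use fatal stroke, recurrent ischemic stroke and TIA, without hemorrhage. The effect falls mainly on the secondary safety outcome. The sensitivity analyses for missing outcomes in 8.1.4 are written for the primary result; they can describe missing data but cannot recover a scan that was never taken.

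It is also fair to say that k/n applies to any missing scan, whatever the cause.

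**Conclusion.** The point holds in a limited form. The exclusion option in 7.5.2 conflicts with the follow-up in 5.7 and, read plainly, with the section's last sentence. A site applying it literally could lose an EOS scan from a patient who was willing to be scanned, for a reason linked to apixaban.

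The number of such patients, and the size and direction of any bias, cannot be determined from the documents. The 1.7 to 5.0 points (60 per arm) or 2.0 to 6.0 points (50 per group) are upper limits under an assumed 1 to 3 patients, not estimates of bias. This is a cheap improvement of minor severity.

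**What to change.** - **7.5.2, individual patients:** replace the option to exclude the patient from the study with permanent discontinuation of study drug, and refer to 5.7 for follow-up.
- **7.5.2, opening sentence:** make clear that, for the individual, the criteria concern study drug.
- **5.7:** state that patients in either arm who stop study drug keep the scheduled visits and the day-14 and EOS MRI or CT unless they withdraw consent, with an EW scan if they leave.
- **Report:** give the number of missing EOS scans by arm.

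The cost is a few sentences and one line in the report. No dosing rule changes and no procedure is added. The downside is that a few patients who are off drug keep attending visits and have a scan that was already scheduled.

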## 5.5 Study Assessments (See figure 1)

The NIHSS and mRS Stroke will be obtained at screening and days 14, 30, 60, 90, 120, 150 and 180. MRI (or CT for subjects with contraindication to MRI) will be obtained at day 14 and EOS or Early Withdrawal (EW).

The Stroke Specific Quality of Life Scale (SS-QOL) will be conducted on screening day and again on day 30 and at EOS or EW.

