## 7.2 Secondary Endpoints

- Any intracranial bleeds assessed by MRI/CT scan at day 14 and EOS or at outcome event.
- Any major bleeds defined as clinically overt bleeding that was accompanied by one or more of the following: a decrease in hemoglobin of 2 g/dL or more; a transfusion of 2 or more units of packed red blood cells; bleeding that occurred in at least one of the following critical sites: intracranial, intraspinal, intraocular, pericardial, intra-articular, intramuscular with compartment syndrome, retroperitoneal; or bleeding that was fatal. Intracranial hemorrhage included intracerebral (hemorrhagic stroke), subarachnoid, and subdural bleeds.

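### Section 7.5.2 words the day-14 hold and 48-hour repeat scan for a silent intracranial hemorrhage for CT subjects only, so a silent non-microbleed bleed on MRI, the default scan, has no stated trigger

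*Combined protocol and SAP*

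**What the plan says.** The follow-up scan is fixed in section 5.5: "MRI (or CT for subjects with contraindication to MRI) will be obtained at day 14 and EOS or Early Withdrawal (EW"). Section 7.5.1 likewise allows CT where MRI is contraindicated. Section 6.4 and the schedule of procedures list MRI or CT without a preference, so 5.5 and 7.5.1 are what make MRI the default.

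Section 7.5.2, under the rules for individual patients, gives four triggers for stopping drug:

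- A general adverse-event rule for apixaban: "In the event of a Grade 3 or higher adverse event attributable to treatment with APIXABAN and not related to the underlying disease".
- A microbleed rule: "if there is any increase in cerebral microbleeds (CMB) at day 14, in either arm, all study medication will be suspended", and the hold lasts "until a repeat MRI is performed 48 hours from day 14 MRI".
- A silent-hemorrhage rule: "In subjects who have a CT scan at day 14 and have a asymptomatic intracranial hemorrhage, all study medication will be suspended", here until a repeat CT at 48 hours.
- A symptomatic rule: "If subjects experience any symptomatic hemorrhagic transformation in either arm, study medication will be suspended".

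After the repeat scan, "Study medication will be restarted in clinically stable individuals".

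The plan also counts bleeds found on either scanner. A secondary endpoint in 7.2 is "Any intracranial bleeds assessed by MRI/CT scan at day 14 and EOS or at outcome event". Section 2.3.2.2 brings asymptomatic imaging findings into the definition of hemorrhagic stroke, and 7.1 lists new hemorrhagic stroke in the primary composite (3.2 and 8.1.2 list a composite without it).

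**The concern.** The rule for a silent hemorrhage is attached to the scanner used for the exception group. A subject scanned by MRI in the ordinary way, with a new silent bleed that is not a microbleed and no rise in microbleeds, meets none of the imaging triggers. The same bleed on CT, or one new microbleed on MRI, would stop the drug and require another scan at 48 hours.

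Intracranial hemorrhage is the main safety question of a trial of early anticoagulation (3.1, 3.3). A mandatory dosing-suspension rule should therefore say what to do for every kind of bleed that the scheduled scan is meant to find. At stake are the safety of the individual subject and consistent handling across four open-label sites.

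**Working it through.** The plan states no figure on this point, so the check is one of coverage: cross the day-14 finding with the scanner and see what 7.5.2 mandates.

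| Day-14 finding | MRI (default) | CT (MRI contraindicated) |
|---|---|---|
| Increase in microbleeds | Hold, repeat MRI at 48 hours | Trigger not limited by scanner; the repeat scan named is MRI |
| Silent hemorrhage other than a microbleed increase | **No mandated hold or repeat scan** | Hold, repeat CT at 48 hours |
| Symptomatic hemorrhagic transformation | Hold | Hold |

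One cell is empty. The next step is to see whether any other provision fills it.

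1. *Grade 3 or higher event (7.5.2).* This covers apixaban only, needs attribution to the drug, and requires no repeat scan. Section 10.4.3 grades by CTCAE where possible; the documents do not reproduce those grades. The fallback wording for Grade 3 describes marked limitation of activity, which a silent finding would not ordinarily meet.
2. *Rule for all patients (7.5.2).* It counts five or more symptomatic transformations on apixaban, so a silent bleed does not enter.
3. *Withdrawal (5.7).* Hemorrhagic transformation is among the reasons a subject may discontinue. The list is permissive.
4. *Adverse-event handling.* Section 10.4 allows an important medical event to be called serious. Section 10.4.1 asks for a report when seriousness is in doubt and for follow-up to resolution or stabilization. Section 10.5.4 asks the same follow-up for non-serious events, and 10.11 has significant worsening on any safety assessment recorded as an event. None orders a hold or a 48-hour scan.
5. *Unscheduled visits (5.6.2).* These start from an event the subject reports; a silent bleed gives nothing to report.
6. *DSMB notice (2.2).* Notice within 24 hours covers unanticipated events and important serious ones, with symptomatic transformation as the example. It is a reporting duty, not a dosing rule.

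The cell stays empty.

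The last step is whether there is drug to hold on that day. The scan falls on day 14 ± 3, that is, days 11 to 17. Time since first dose, if dosing starts on schedule, runs from (11 − latest start) to (17 − earliest start):

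| Group | Start window (day) | Days since first dose at the scan |
|---|---|---|
| Apixaban, TIA | 0 to 3 | 11 − 3 = 8 to 17 − 0 = 17 |
| Apixaban, small stroke | 3 to 5 | 11 − 5 = 6 to 17 − 3 = 14 |
| Apixaban, medium stroke | 7 to 9 | 11 − 9 = 2 to 17 − 7 = 10 |
| Warfarin, TIA | 2 to 12 | 11 − 12 = −1 to 17 − 2 = 15 |
| Warfarin, small or medium stroke | 9 to 19 | 11 − 19 = −8 to 17 − 9 = 8 |

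Every apixaban subject started on schedule is already on drug at the scan. Some warfarin subjects may not have started (negative values); for them the equivalent action is to defer the first dose, which the present text does not mention.

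**The case against.** The strongest reply is that the two imaging sentences are a matched pair. Elsewhere the protocol pairs the same markers: exclusion 11 sets microbleeds on gradient-echo MRI beside hemorrhage on CT, and 2.3.2.2 sets gradient-echo microbleeds beside CT hyperintensities. On that reading the authors named the MRI marker and the CT marker of one idea, silent bleeding on imaging, and set the MRI threshold at the smallest finding. An investigator told to stop drug for one new microbleed would hardly continue through a larger bleed. The adverse-event provisions, investigator judgement, and the examinations with NIHSS and mRS at days 30, 60, 90, 120 and 150 all make unnoticed continued dosing less likely.

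Much of this stands. It makes a drafting gap the likely explanation, and a reader who inferred a deliberate choice to dose through silent MRI bleeds would go beyond the documents. It does not change what the rule says. The pairing has to be inferred, and none of the other provisions makes a hold or a repeat scan compulsory.

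**Conclusion.** The gap is real as a matter of wording. As written, 7.5.2 treats a new silent non-microbleed hemorrhage on the default scanner less cautiously than one new microbleed or the same bleed on CT. This rests on a literal reading and on MRI being the default under 5.5 and 7.5.1. The number of subjects affected cannot be derived, because the documents give neither the share scanned by MRI nor the rate of such bleeds.

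Three stronger readings are not supported:

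- *That such a bleed goes unwatched until the end-of-study scan.* The interval between scheduled scans is not a period without monitoring, given the intervening visits and the adverse-event follow-up, either of which may prompt earlier imaging.
- *That the gap biases the comparison of arms.* The imaging rules are not written differently by arm, and nothing in the documents shows a differential effect.
- *That the restart rule is also wrong because it names clinical stability and not the repeat-scan result.* The text leaves interpretation of that scan to the physician. The documents offer no imaging threshold for restart, and setting one is a clinical preference on which reasonable people differ.

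**What to change.** Replace the two imaging triggers in 7.5.2 with one: *any increase in cerebral microbleeds or any new asymptomatic intracranial hemorrhage on the day-14 MRI or CT, in either arm*. Keep the existing hold and the existing 48-hour repeat scan, and state that the repeat uses the same modality as the day-14 scan. Add that if warfarin has not yet started, its first dose is deferred until the repeat scan. Leave the restart wording as it is.

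This is a change of protocol wording only. The day-14 scan is already scheduled, and the hold and repeat scan already exist. The downside is a few more repeat scans and a few more periods of about 48 hours without study anticoagulant in subjects with atrial fibrillation and a recent TIA or stroke.

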#### For all patients

In the event of five or more patients experiencing a symptomatic hemorrhagic transformation in the APIXABAN arm and not related to the underlying disease, dosing will be suspended in all patients to allow analysis and determination whether to continue the treatment, alter dose regimen or to terminate the study.

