## 2.2 Data and Safety Monitoring Board

The DSMB is responsible for safeguarding the interests of study participants, assessing the safety and efficacy of study procedures, and for monitoring the overall conduct of the study. The recommendations will be forwarded to the Executive Committee and the sponsor for final decision.

The DSMB is an independent group advisory to the executive board and is required to provide recommendations about continuing, and stopping the study. In addition, the DSMB is asked to make recommendations, as appropriate, about the benefit/risk ratio of procedures and participant burden

The DSMB will convene annually and at the milestones of 40 and 80 patients enrolled as well as at study conclusion to review safety data.

Notification of and referral for abnormal findings Data will be collected by the research team. Study data will be entered into the data collection forms or recorded electronically as they are collected during the study visit. The PIs will monitor all data for any inconsistencies or irregularity. If unanticipated adverse events or SAE of importance (symptomatic hemorrhagic transformation) are observed, they will be reported to the DSMB within 24 hours. All other AE's will be reported during scheduled meetings and to the IRB according to standard AE reporting policies. The Principal Investigator will forward all decisions to the regulatory authority as appropriate.

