##### Assessment of Causality

The investigator will attempt to explain each SAE and assess its causal relationship, if any, to the Study Medication . The degree of certainty with which an SAE can be attributed to Study Medication (or alternative causes, e.g. natural history of the underlying diseases, concomitant therapy, etc.) will be determined by how well the event can be understood in terms of one or more of the following:

- Reaction of similar nature having previously been observed with this type of medication.
- The event having often been reported in literature for similar types of medication.

The investigator will assess causality of all AEs, using the following method:

In your opinion, is there a reasonable possibility that the AE may have been caused by the study medication?

- No.
  - **Unrelated:** there is no suspicion that there is a relationship between Study Medication and AE, there are other more likely causes and the Study Medication is not suspected to have contributed to the AE.
- Yes.
  - **Related:** there is suspicion of a relationship between the study medication and AE (without determining the extent of probability); there are no other more likely causes and study medication is suspected to have contributed to the AE.

Events considered related to the study medication will be further classified as follows:

**Probable**-- AE cannot be reasonably explained by other factors (i.e. clinical condition, environmental/toxic factors or other treatments)

**Possible**-- AE can be reasonably explained by other factors (as mentioned above)

**Unlikely**-- AE occurs within an unusual time frame of administration of study medication and can also be reasonably explained by other factors (as mentioned above)

Non-serious and serious AEs will be evaluated as 2 distinct types of events given their different medical nature. If an event meets the criteria to be determined "serious", it will be examined by the investigator to the extent to be able to determine ALL contributing factors applicable to each SAE.

Other possible contributors include:

- Underlying disease
- Other medication
- Protocol required procedure
- Other cause (specify)

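### The five-patient suspension trigger counts a symptomatic hemorrhagic transformation only if it is judged unrelated to the underlying disease, a test that fits this event badly; an on-treatment condition should replace it

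*Combined protocol and SAP*

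**What the plan says.** Section 7.5.2 has two levels.

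- **Whole trial.** The trigger is "five or more patients experiencing a symptomatic hemorrhagic transformation in the APIXABAN arm and not related to the underlying disease". When it is met, "dosing will be suspended in all patients to allow analysis and determination whether to continue the treatment", alter the regimen or terminate. The section does not say who applies the relatedness condition or by what standard.
- **Individual patient, general rule.** Apixaban is suspended for a Grade 3 or higher adverse event that is "attributable to treatment with APIXABAN and not related to the underlying disease". The relatedness phrase is the same, but here it is paired with attribution to the drug. The whole-trial rule omits that half.
- **Individual patient, same event.** "If subjects experience any symptomatic hemorrhagic transformation in either arm, study medication will be suspended". There is no relatedness condition.

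Section 2.2 also handles the event without a filter: if unanticipated adverse events or "SAE of importance (symptomatic hemorrhagic transformation) are observed, they will be reported to the DSMB within 24 hours". That section gives the DSMB meeting milestones (40 and 80 enrolled) but no numeric boundary. Section 8.2 plans no interim analysis.

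The nearest procedure for judging relatedness is section 10.4.2: "The investigator will assess causality of all AEs, using the following method". Part of its definition of a related event is that "there are no other more likely causes and study medication is suspected to have contributed to the AE".

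**The concern.** The usual meaning of hemorrhagic transformation is bleeding into the infarct that brought the patient into the trial. That infarct is the underlying disease or its direct result, so it is nearly always a plausible contributor. A filter that drops events related to the underlying disease therefore tends to drop the events the rule names.

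The filter also puts the causality question in the wrong place. The rule already provides a review after suspension, in which causality can be weighed with all cases in view. Applying it at the count means the review may never start.

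The trial starts apixaban earlier than conventional practice, and section 1.2 calls the evidence on early anticoagulation limited. The point at stake is whether five symptomatic bleeds on early apixaban would set off the pause that the protocol appears to promise.

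**Working it through.** **1. No figure to reproduce.** The documents give no assumed bleed rate, target probability or derivation for the threshold of five.

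**2. Inputs from the documents.**
- Apixaban arm: 120 randomized 1:1 (section 4.1), so 60. Five of 60 is 8.3%.
- Long-term apixaban intracranial bleed rate: 0.33% per year (section 1.1 table). Over 180 days this is 0.33% × 180/365.25 = 0.16%, and 60 × 0.0016 is about 0.1 expected event.
- Patients with an index infarct: four blocks of 10 per stroke-type stratum (section 8.1.6) gives 40 per stratum, 20 per arm. Small plus medium stroke gives about 40 on apixaban.

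**3. Assumptions.** The documents give neither the early-start rate *r* of symptomatic transformation nor the share *s* of events that would be excluded. Both are shown over a range, with each event excluded independently.

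**4. Given the number of events.** With *k* events, the number counted is Bin(*k*, 1 − *s*), and the rule fires if five or more count.
- *k* = 5: all five must count, so P = (1 − *s*)^5. This is 0.9^5 = 0.59, 0.75^5 = 0.24 and 0.5^5 = 0.03. Without the filter it is 1. One exclusion is enough to block the trigger.
- *k* = 8: P = Σ C(8, j)(1 − *s*)^j *s*^(8 − j) for j = 5 to 8. This is 0.995, 0.89 and 0.36 for *s* = 0.1, 0.25 and 0.5. For *s* = 0.5 it is (56 + 28 + 8 + 1)/256 = 0.36.

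**5. Given a true rate.** P(X ≥ 5), with X ~ Bin(60, *r*(1 − *s*)):

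| True rate *r* | None excluded | A quarter excluded | Half excluded |
|---|---|---|---|
| 3% | 3.4% | 1.1% | 0.2% |
| 5% | 18% | 7% | 2% |
| 10% | 73% | 47% | 18% |

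The true rate needed for an 80% chance of firing is 11.0%, 14.6% and 21.9% in the three columns. If only the 40 infarct patients are at risk, the 10% row becomes 37%, 18% and 5%.

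**6. The drug-attribution reading.** Section 10.4.2 asks whether there is a reasonable possibility that the drug caused the event. It then defines Related partly by the absence of any likelier cause. It next divides related events into classes, of which *Possible* covers events that other factors, including the clinical condition, could reasonably explain. A bleed into the index infarct fails the second test, because the infarct is a ready alternative cause, yet it fits *Possible*. Two careful investigators could classify the same bleed differently, each knowing the treatment arm.

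**7. What bare deletion would do.** Section 5.2 places randomization within 48 hours of symptoms. Section 5.3 starts apixaban on day 3-5 after a small stroke and day 7-9 after a medium stroke. A medium-stroke patient so randomized is in the apixaban arm for at least 7 − 2 = 5 days before any apixaban. A transformation in that interval cannot be caused by the drug and should not count.

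**The case against.** The strongest reply has five parts.

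- **The filter has a legitimate use.** It screens out bleeds before the first dose. This stands, and it rules out simple deletion. A first-dose condition does that job without a causality judgment.
- **Section 10.4.2 does not force exclusion.** An event with a plausible alternative cause can still be related, in the *Possible* class, and section 10.3 gives a looser test. This also stands. A reader might infer that the trigger can never fire. The documents do not support that: it follows only if every event is attributed to the infarct, and the wording leaves room for the opposite judgment. What they show is an undefined filter with an inconsistent standard behind it.
- **The rule counts one arm with no comparator.** Attribution is then its only guard against background bleeding. If an assumed 5% rate were all background, removing a filter that excludes half would raise false firing from 2% to 18%. This is a real cost, though firing opens a review and does not end the trial.
- **The size rests on assumed inputs.** This is true. The long-term rate gives about 0.1 expected event, and at 3% or below the threshold of five dominates. The filter matters only if early treatment bleeds well above the long-term rate, which is the case the trigger is for.
- **Oversight without a filter already exists.** This is also true. The DSMB is told within 24 hours and can recommend stopping. Sections 10.4.1 and 10.5 send serious events to the funder and the IRB. A reader might infer that safety oversight as a whole fails; it does not.

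A reader might also infer that the trigger must cover every intracranial hemorrhage. Transformation is undefined, and the day 14 CT rule uses the broader term: subjects who "have a asymptomatic intracranial hemorrhage, all study medication will be suspended until a repeat CT is performed". But a gap for TIA patients arises only on a narrow reading. Widening the trigger would be a new rule, for the sponsor to choose.

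**Conclusion.** The point holds as a defect in the wording of the trial's only numeric trial-level trigger; no DSMB charter is among the documents. Read literally, the relatedness condition can remove most or all of the events it is meant to count. Read as drug attribution, it hands the count to an open-label investigator under an inconsistent standard. Either way it departs from how the same protocol treats the same event for the individual patient and for the DSMB.

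The practical size depends on the excluded share, which is unknown, and on the true rate exceeding about 3%. The change is worth making because it is cheap and concerns patient safety, but it is a modest improvement to the automatic trigger.

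**What to change.** In 7.5.2 (For all patients), replace the closing relatedness condition with *after the first dose of apixaban*, so that every on-treatment symptomatic hemorrhagic transformation in the apixaban arm counts. Judge causality in the review that follows suspension. Keep the threshold of five.

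This is a one-sentence amendment, with a matching line in the DSMB charter if one exists. It needs no new data, assessments or patients. The price is a somewhat higher chance of a temporary trial-wide pause in anticoagulation, in patients with AF and a recent stroke or TIA, for bleeds later judged to be background. Prompt DSMB review would keep that pause short.
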